9.1.8.1 Agent Inventory Records

The investigator, or a responsible party designated by the investigator, must maintain a careful record of the receipt, dispensing and final disposition of all agents received from the PMB using the appropriate NCI Investigational Agent (Drug) Accountability Record (DARF) available on the CTEP forms page. Store and maintain separate NCI Investigational Agent Accountability Records for each agent, strength, formulation and ordering investigator on this protocol.

9.1.9 **Investigator Brochure Availability**

The current versions of the IBs for the agents will also be accessible to site investigators and research staff through the PMB Online Agent Order Processing (OAOP) application. Access to OAOP requires the establishment of a CTEP Identity and Access Management (IAM) account and the maintenance of an "active" account status, "current" password, and active person registration status. Questions about IB access may be directed to the PMB IB coordinator via email.

10.0 CRITERIA FOR REMOVAL FROM PROTOCOL THERAPY AND OFF STUDY CRITERIA

10.1 Criteria for Removal from Protocol Therapy

- a) Clinical (including physical examination or serum tumor markers) or radiographic evidence of progressive disease (See Section 12).
- b) Adverse Events requiring removal from protocol therapy (See Section 6).
- c) Refusal of protocol therapy by patient/parent/guardian
- d) Non-compliance that in the opinion of the investigator does not allow for ongoing participation.
- e) Completion of 26 cycles of therapy.
- f) Physician determines it is not in the patient's best interest.
- g) Repeated eligibility laboratory studies (CBC with differential, bilirubin, ALT (SGPT) or serum creatinine) are outside the parameters required for eligibility prior to the start of protocol therapy (See Section 8.1).
- h) Study is terminated by Sponsor.
- i) Pregnancy
- j) Patient did not receive protocol treatment after study enrollment

Patients who are removed from protocol therapy during cycle 1 should continue to have the required observations in Section 8.1 until the originally planned end of the cycle or until all adverse events have resolved per Section 13.4.4, whichever happens LATER. The only exception is with documentation of the patient's withdrawal of consent from the APEC1621SC screening protocol. Patients who are removed from protocol therapy in subsequent cycles should have the necessary observations to ensure adequate clinical care.

10.2 Follow-Up Data Submission and APEC1621SC Off Study Criteria

Patients who are off subprotocol therapy will initially be followed on the therapeutic subprotocol for a 30-day period. During follow-up on the therapeutic subprotocol ongoing adverse events, or adverse events that emerge after the patient is removed from protocol therapy, but within 30 days of the last dose of investigational agent, must be followed and reported via RAVE and CTEP-AERS (if applicable). Upon completion of subprotocol follow-up period, the patient will continue to be followed on the APEC1621SC screening protocol. Follow-up data submission will occur until one of the APEC1621SC Off Study Criteria is met (See Section 10 of APEC1621SC for details); consent is withdrawn or the patient dies or is lost to follow-up.

11.0 STATISTICAL AND ETHICAL CONSIDERATIONS

11.1 Sample Size and Study Duration

APEC1621M will require a minimum of 20 evaluable patients and a maximum of 49 patients, allowing for 15% inevaluability. Assuming an enrollment rate of 2-9 biomarker positive patients per year, the primary cohort of this subprotocol is expected to be completed within 2.7-12 years.

11.2 **Dosing Considerations**

11.2.1 Pediatric MATCH Sub-arm Dosing in the Absence of Pediatric Phase 1 Data

Please see Section 5.1 for a specific discussion of the dosing of tipifarnib to be used in this study. If there is no prior pediatric phase 1 data, study investigators will review relevant data with the pharmaceutical partner to identify a drug specific dosing plan for testing in children with relapsed or refractory cancer, and trial participants will be closely monitored to ensure tolerability of the selected dose. Limited pharmacokinetic sampling may be done for patients enrolled on these arms. In general, the dosing for the Pediatric MATCH subprotocols will follow the guidelines below:

• For agents for which the adult RP2D is below the adult MTD, the adult RP2D (normalized to body surface area or body weight) will be used for evaluation in the Pediatric MATCH, understanding that further dose optimization may be required in a future pediatric study.

11.3 Study Design

The primary cohort and any biomarker negative expansion cohorts defined below will employ single stage A'Hern designs of N=20 and N=10 respectively. The agent will be deemed worthy of further study in the relevant subset of patients (i.e. biomarker positive in any histology, biomarker positive in a particular histology, etc) if the decision rule is met. Operating characteristics are shown below.

Cohort	N	Decision Rule	Alpha	Power
Primary biomarker positive		≥ 3 responses	10%	90%

Histology-specific biomarker positive expansion cohorts will, by definition, be deemed worthy of further study, since they will have at least 3 responses. The table below shows 90% confidence intervals (Wilson method) for a range of observable response rates.

Cohort Size Observed Response Rate		90% Confidence Interval	
10	30%	13% - 56%	
10	40%	19% - 65%	
10	50%	27% - 73%	

11.3.1 **Primary Cohort**:

APEC1621M will evaluate a primary cohort of 20 mutation-matched ("biomarker positive") evaluable patients of any histology for the primary study aim of determining the objective response rate (CR/PR according to the response criteria in Section 12.3) to the agent. Using an A'Hern design⁵³ with alpha=10%, a sample of N=20 will provide 90% power to detect an improvement in response rate from 5%, if the treatment is ineffective, to 25% if the targeted therapy is sufficiently effective to warrant further study. If there are at least 3 responses out of 20 in the primary cohort, the biomarker/therapy match will be deemed a success.

11.3.2 Histology-Specific Biomarker Positive Expansion Cohorts:

If ≥ 3 patients in the primary cohort with the same histology show signs of objective response (CR/PR according to the response criteria in Section 12.3), a histology-specific biomarker positive expansion cohort will open after the primary cohort is completed to up to 7 evaluable patients for a total sample size of 10 evaluable biomarker positive patients with that histology. This will allow us to estimate more precisely the activity in biomarker positive patients of that histology. See

We will open up to 3 such expansion cohorts for biomarker positive patients (i.e., if 3 histologies have \geq 3 responses, we will open a total of 3 expansion cohorts as described above). Note that this can only happen if the response rate in the primary cohort is at least 45% (9/20) and there cannot be more than 21 additional evaluable patients in total for these expansion cohorts.

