In preliminary analysis of Pediatric MATCH trial data performed on 3/18/20, a total of 37 activating RAS mutations were identified in 769 patients screened, including 6 HRAS mutations in rhabdomyosarcomas. Other sequencing efforts have also identified a small number of cases of HRAS mutations in pediatric solid tumors. These include: 1) the Foundation Medicine Pediatric Portal²⁰ has 4 total cases of HRAS mutation (of total 1215), and of these, 3 are in embryonal RMS; 2) cBioPortal has a total of 109 cases of HRAS mutations²¹ (of total 10,000 cases, frequency 1.1%), and of these, 2 were embryonal RMS and 1 was neuroblastoma; 3) the TARGET neuroblastoma data set²² has 3 cases of HRAS CNG (out of 1089 total), but no SNV detected in this cohort; 4) the GAIN/ iCAT2 cohort has identified 2 cases of HRAS mutant RMS (out of total 250 total tumors, [name], personal communication); and 5) a comprehensive genomic profiling study of RMS²³ revealed HRAS mutations in 2 of 43 total RMS cases.

The three classical RAS genes encode four highly related guanine nucleotide binding proteins: HRAS, KRAS4A, KRAS4B and NRAS. RAS proteins function as guanine nucleotide-regulated binary on-off switches. In normal quiescent cells, RAS is predominantly GDP-bound and inactive. Growth factors activate RAS-selective guanine nucleotide exchange factors (RAS-GEFs; e.g., SOS1, SOS2) to promote nucleotide exchange and formation of active RAS-GTP, a reaction that requires RAS be localized to the plasma membrane. Once in the active, GTP-bound conformation,

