11.4 Methods of Analysis

Response criteria are described in Section 12. A responder is defined as a patient who achieves a best response of PR or CR on the study. Response rates will be calculated as the percent of evaluable patients who are responders, and confidence intervals will be constructed using the Wilson score interval method.⁵⁴ Decision making for A'Hern design cohorts will follow rules described above.

Toxicity tables will be constructed to summarize the observed incidence by type of toxicity and grade. A patient will be counted only once for a given toxicity for the worst grade of that toxicity reported for that patient. Toxicity information recorded will include the type, severity, time of onset, time of resolution, and the probable association with the study regimen.

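### Histology expansion cohorts pool the responders that triggered opening into the 10-patient rate and report it with an ordinary Wilson 90% interval, so when patients are added the rate is biased upward and the interval under-covers at low-to-moderate true rates

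*Combined protocol and SAP*

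**What the plan says.** The trigger and the pooling are both in Section 11.3.2. A cohort opens if at least 3 "patients in the primary cohort with the same histology show signs of objective response". It will then "open after the primary cohort is completed to up to 7 evaluable patients for a total sample size of 10 evaluable biomarker positive patients" of that histology. The patients who produced the trigger therefore stay in the 10, and Section 11.3 relies on this: "Histology-specific biomarker positive expansion cohorts will, by definition, be deemed worthy of further study, since they will have at least 3 responses".

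The stated purpose is estimation: "This will allow us to estimate more precisely the activity in biomarker positive patients of that histology".

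On reporting, Section 11.3 says: "The table below shows 90% confidence intervals (Wilson method) for a range of observable response rates". The table gives 13%-56%, 19%-65% and 27%-73% for observed rates of 30%, 40% and 50% in 10 patients. Section 11.4 applies one rule to all response rates: "Response rates will be calculated as the percent of evaluable patients who are responders", and "confidence intervals will be constructed using the Wilson score interval method". Neither section makes an exception for cohorts that exist only because they responded, asks for the added patients to be shown separately, or notes the effect of selection on the rate or the interval.

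**The concern.** A Wilson interval has roughly its stated coverage when the 10 patients are an unselected sample. Here the first m of them are seen only if at least 3 responded. Low outcomes are cut off, so the pooled rate is too high on average given opening, and the interval tends to miss from above. In a 10-patient cohort the rate cannot be below 3/10 and the lower limit cannot be below 12.7%. The interval thus always excludes the design's 5% null rate, whatever the truth.

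What is at stake is the one thing the expansion is meant to deliver, an estimate of activity in a named histology. A reader of the eventual report would take the rate and its 90% interval at face value.

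**Working it through.** **Inputs.** Trigger of at least 3 responses, total of 10, Wilson method, 90% level: Sections 11.3, 11.3.2 and 11.4. Primary cohort of 20 and target rate of 25%: Section 11.3.1. Two quantities are assumptions because the documents do not give them: m (same-histology evaluable patients among the primary 20) and p (the true response rate in that histology).

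**The plan's own figures.** The Wilson 90% interval with n = 10 and z = 1.645 gives 12.7%-55.8% for 3/10, 19.4%-64.8% for 4/10 and 26.9%-73.1% for 5/10. These match the table. The arithmetic is right for an unselected 10.

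**Model.** X ~ Bin(m, p) given X ≥ 3; Y ~ Bin(10 − m, p), independent; pooled rate (X + Y)/10. Coverage is the probability, given X ≥ 3, that the Wilson interval for X + Y responses in 10 contains p.

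**By hand, m = 3, p = 25%.** Given opening, X = 3. The mean rate is (3 + 7 × 0.25)/10 = 47.5%. The interval contains 25% only at 3/10 or 4/10, because at 5/10 it starts at 26.9%. Coverage is P(Y ≤ 1) = 0.75^7 + 7 × 0.25 × 0.75^6 = 0.1335 + 0.3115 = 44.5%. At p = 15% only 3/10 covers, because 4/10 starts at 19.4%, so coverage is 0.85^7 = 32%.

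**Exact enumeration.**

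| m | patients added | chance of opening, p = 25% | mean rate, p = 25% | coverage, p = 25% | coverage, p = 15% |
|---|---|---|---|---|---|
| 3 | 7 | 1.6% | 47.5% | 44.5% | 32% |
| 5 | 5 | 10% | 44% | 57% | 41% |
| 8 | 2 | 32% | 39.5% | 76% | 58% |
| 10 | 0 | 47% | 37% | 83.5% | 72% |
| unselected 10 | – | – | 25% | 87% | 95% |

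**Where the effect fades.** For m = 8, 9 and 10, coverage is 89%, 91% and 92% at p = 30% (unselected 92%), and 92%, 93% and 93% at p = 40% (unselected 90%). With m = 3, coverage is 71% at p = 40% and 84% at p = 60%, but for m = 3 or 4 it is 91% or more at p = 70%, 80% and 90%.

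**How often patients are added.** Assume that one histology has share s of the primary 20, with m ~ Bin(20, s). The chance that a cohort opens and adds someone is the sum over m = 3 to 9 of P(m) × P(X ≥ 3 given m). At p = 25% this is about 12% for s = 25%, 13% for s = 50% and 0.15% for s = 75%. The same sum over all m gives 13%, 46% and 75%; the difference is made up of cases that add nobody. Weighting the m-specific results by the terms of the m = 3 to 9 sum, the mean rate is 42% and coverage 66% at s = 25%, and 39% and 76% at s = 50%.

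**Check of the remedy.** Post-trigger patients are not response-selected. Wilson 90% on them alone covers 88%-97% with 7 patients and 84%-97% with 5, for p from 10% to 40%.

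**The case against.** The best defence has four parts.

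- **The selection is in plain sight.** Section 11.3 says outright that every such cohort has at least 3 responses, and its table starts at 30%. A reader might infer concealment; the text does not support that. But disclosing the trigger does not correct the mean or the coverage, and the table carries no qualification.
- **Nothing is decided on these figures.** The expansion has no alpha, power or test, and any histology with 3 responders has already met the primary rule of 3 in 20. This stands, and it limits the severity.
- **The worst cases are rare.** This also stands. At p = 25% and m = 3 a cohort opens 1.6% of the time. In a cohort of 10, coverage is 0% at any true rate below 12.7%, but at p = 10% the chance of opening is only 0.1% to 7% for m from 3 to 10. The zero should not be read as a frequent error. Still, the interval is read only when a cohort opens, so its behaviour given opening is what matters.
- **Rhabdomyosarcoma may dominate, making m large.** Section 2.1.1 reports "a total of 37 activating RAS mutations were identified in 769 patients screened, including 6 HRAS mutations in rhabdomyosarcomas", which makes this plausible, and additions would then almost never happen. Appendix VII, however, lists 20 tumor-type categories, so m could be small in another histology.

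Section 11.3.2 does not say how a total of 10 is formed when m exceeds 10, so any coverage figure for that case would rest on an invented rule. None is relied on here.

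**Conclusion.** The concern holds for cohorts that add patients, that is, m from 3 to 9. Given opening, the pooled rate overstates activity on average: by 22.5, 19 and 14.5 points at a true 25% for m = 3, 5 and 8. The nominal 90% interval under-covers at low-to-moderate true rates, most severely when m is small. These sizes rest on assumed m and p and on independent responses with a common rate within the histology.

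Three stronger readings might be inferred and are not supported:

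- **That small m alone spoils the interval.** It does not at true rates of 70% or more. Nor is the loss material for m of 8 to 10 at about 30% or more.
- **That the tabulated intervals are miscalculated.** They are correct for 10 unselected patients.
- **That the trial's main conclusion is biased.** The 20-patient response rate and its decision rule do not use the expansion data, and no go/no-go rule uses the expansion interval.

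This is a minor-to-moderate reporting defect in a contingent analysis.

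**What to change.** Amend Sections 11.3, 11.3.2 and 11.4 so that, for each opened histology:

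1. m is reported.
2. The primary-cohort (trigger) patients and the post-trigger patients are reported separately, with a Wilson 90% interval for the post-trigger patients.
3. The pooled 10-patient rate and the Section 11.3 interval table are labelled as conditional on at least 3 responses and as not having nominal 90% coverage.
4. The text states that the judgement that the histology merits further study rests on the trigger alone and is not confirmed by the added patients.

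An interval computed conditionally on the trigger could be added but is not required. It can be uninformative: at m = 8 and 3/10 the exact version runs from 0% to 53%.

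The cost is wording and slightly more analysis, with no extra patients. Added patients enrol after the primary cohort is complete, so they can already be told apart. The downsides are less favourable figures and thin post-trigger data when m is large: m = 8 adds 2 patients, and 0/2 gives 0%-57%. When m is 10 or more nobody is added and only the label remains.

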2.3.1.2 Solid Tumors

In the ongoing Phase 2 study in HRAS-mutant solid tumors, KO-TIP-001, 48 patients have been treated with tipifarnib. Cohort 1 (HRAS-mutant thyroid cancer) has been closed to active accrual due to lack of efficacy. However, there have been 4 confirmed responses in 14 evaluable patients in stage 1 of Cohort 2 of the study (HRAS-mutant other solid tumors). All responses in Cohort 2 were observed in patients with HRAS mutant HNSCC. These responses were rapid and durable, with 3 responses of > 1.5 yrs in duration. Responses were observed in patients with disease resistant to chemotherapy, cetuximab and immunotherapy. Based on these data, enrollment of patients with HRAS mutant HNSCC has been extended in this cohort (stage 2) to a target of 30 patients with HRAS missense variations expressed at high variant allele frequency (VAF; at least 35% or a minimum of 20% if that patient's baseline serum albumin was least 3.5 mg/dL at the time of tumor biopsy). In stage 2 of the trial, partial responses were noted in 10 of 18 evaluable patients and the remaining 8 patients had a best response of stable disease. Partial responders had a median progression-free survival (PFS) of 8.3 months, and those with stable disease had a median PFS of 4.5 months, which compared favorably to the PFS of 3.2 months for these patients prior to enrollment on KO-TIP-001. Enrollment continues in this cohort, and additionally another cohort (HRAS mutant SCC, excluding HNSCC) was added to the protocol and is currently enrolling. 26,48

In the ongoing pivotal study in HRAS mutant HNSCC, KO-TIP-007 (AIM-HN/SEQ-HN), no patients have yet been treated with tipifarnib and therefore no preliminary data are available for this study.^{26,48}

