2.4 Pediatric Studies

2.4.1 Prior Experience in Children

Tipifarnib has been well tolerated in pediatric patients, but the activity of tipifarnib in pediatric malignancies to date has been disappointing. 40-42,45,46 For example, in a phase I trial of tipifarnib in children with solid tumors or neurofibromatosis type 1 (NF1)-associated plexiform neurofibromas, the maximum tolerated dose (MTD) was determined to be 200 mg/m²/dose given twice daily for 21 days, repeated every 28 days. 41 The observed dose limiting toxicities (DLT) in Cycle 1 were myelosuppression, rash, nausea, vomiting and diarrhea, and no cumulative toxicities were observed. Although the farnesyltransferase activity at the MTD, determined by the percent HDJ2 prenylation in peripheral blood mononuclear cells (PBMCs) was 30% of baseline, no objective responses were observed. 41 Similarly, a phase I trial of tipifarnib in children with leukemia, used a dose of 300 mg/m2/dose given twice daily for 21 days, repeated every 28 days, with observed DLTs of rash, mucositis, and nausea, vomiting and diarrhea. Importantly, neurotoxicity, which was dose limiting in adult patients, was not observed in pediatric patients treated with tipifarnib. 40 Again, although farnesyltransferase activity was inhibited in leukemic blasts, no objective responses to tipifarnib

treatment were observed in this study. Tipifarnib also failed to show clinical benefit in phase II studies in pediatric patients with diffuse intrinsic pontine glioma (DIPG), juvenile myelomonocytic leukemia (JMML) or NF1-associated plexiform neurofibromas. ^{42,45,46}

The lack of response to tipifarnib in pediatric malignancies may have been, in part, because these trials were conducted without genomic pre-selection of treatment subjects to include only patients with somatic *HRAS* mutations. The study in patients with JMML was the only study of tipifarnib in pediatric patients to identify somatic driver mutations in enrolled patients, but *HRAS* mutations were not among the panel of genes tested. Recently, promising activity of tipifarnib has been demonstrated in adult patients with HRAS-driven head and neck squamous cell carcinoma (HNSCC). ⁵² Tipifarnib may be similarly effective in pediatric patients with mutant HRAS-driven tumors.

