8.0 EVALUATIONS/MATERIAL AND DATA TO BE ACCESSIONED

8.1 Required Clinical, Laboratory and Disease Evaluation

All clinical and laboratory studies to determine eligibility must be performed within 7 days prior to enrollment unless otherwise indicated. Laboratory values used to assess eligibility (see Section 4.0) must be no older than seven (7) days at the start of therapy. Laboratory tests need **not** be repeated if therapy starts **within** seven (7) days of obtaining labs to assess eligibility. If a post-enrollment lab value is outside the limits of eligibility, or laboratory values are older than 7 days, then the following laboratory evaluations must be re-checked within 48 hours prior to initiating therapy: CBC with differential, bilirubin, ALT (SGPT) and serum creatinine. If the recheck is outside the limits of eligibility, the patient may not receive protocol therapy and will be considered off protocol therapy. Imaging studies, bone marrow aspirate and/or biopsy, must be obtained within 14 days prior to start of protocol therapy (repeat the tumor imaging if necessary).

STUDIES TO BE OBTAINED	Pre- Study	During Cycle 1	Prior to Subsequent Cycles^
History	X	Weekly	X
Physical Exam with vital signs	X	Weekly	Cycle 2 Day 1 and Cycle 2 Day 15; then prior to all subsequent cycles
Height, weight, BSA	X		X
Performance Status	X		
Pregnancy Test ¹	X		
CBC, differential, platelets	X	Weekly ^{2,3}	Cycle 2 Day 1 and Cycle 2 Day 15; then prior to all subsequent cycles ^{2,3}
Urinalysis	X		
Electrolytes including Ca++, PO ₄ , Mg++	X	Weekly	X
Creatinine, ALT, bilirubin	X	Weekly	X
Albumin	X		X
Tumor Disease Evaluation ^{4-A, 4-B, 4-C}	X		Every other cycle x 3 then q 3 cycles ⁴
Bone Marrow Aspirate and/or biopsy ^{5,6}	X		E.S.E. allen
Medication Diary ⁷		Weekly	X

Studies may be obtained within 72 hours prior to the start of the subsequent cycle.

Women of childbearing potential require a negative pregnancy test prior to starting treatment; sexually active patients must use an acceptable method of birth control. Abstinence is an acceptable method of birth control.

If patients have Grade 4 neutropenia then CBCs should be checked at least every other day until recovery to Grade 3 or until meeting the criteria for dose limiting toxicity.

³ If patients develop Grade 3 or higher thrombocytopenia then CBCs should be checked every 3-4 days until recovery per Section 6.1

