- Tumor Disease Evaluation should be obtained on the next consecutive cycle after initial documentation of either a PR or CR. Subsequent scans may restart 2 cycles after the confirmatory scan. If the institutional investigator determines that the patient has progressed based on clinical or laboratory evidence, he/she may opt not to confirm this finding radiographically.
- 4-A Neurological exam also required for CNS patients.
- 4-B Non- Hodgkin Lymphoma/ Histiocytosis patients are required to have PET scans within 2 weeks prior to start of therapy and should also be followed with PET scans if positive at diagnosis. Refer to Section 12.8
- Patients with neuroblastoma must have both CT/MRI and MIBG scintigraphy prior to the start of protocol therapy if the patient was enrolled with or has a history of having MIBG avid tumor. Otherwise the patient must have either FDG-PET/CT or PET/MR prior to the start of protocol therapy. For patients with neuroblastoma and measurable disease by CT or MRI, lesions should be measured and followed using the same modality (CT or MRI) in addition to MIBG or FDG-PET/CT. For patients with neuroblastoma and evaluable disease by MIBG scintigraphy, use the same modality (MIBG scintigraphy) to image and follow patients; CT/MRI are not required but may be performed as clinically indicated. Refer to Section 12.5 and Section 12.8:
- Bone marrow aspirate and/or biopsy only required in patients suspected of having bone marrow metastasis on the basis of history, symptoms, laboratory evaluation or other clinical data.
- Bone marrow aspirate and/or biopsy should be performed only when complete response or partial response is identified in target disease or when progression in bone marrow is suspected.
- 7. The medication diary should be collected and reviewed weekly during cycle 1 (medication). The medication diary should also be reviewed after completion of each treatment cycle and uploaded into RAVE.

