11.5 Evaluability for Response

Any eligible patient who is enrolled and receives at least one dose of protocol therapy will be considered evaluable for response. Any patient who receives non-protocol anti-cancer therapy during the response evaluation period will be considered a non-responder for the purposes of the statistical rule, unless they show an objective response prior to receiving the non-protocol anti-cancer therapy (in which case they will be considered a responder). Patients who demonstrate a complete or partial response confirmed by central review will be considered to have experienced a response. All other patients will be considered non-responders. Patients who are not evaluable for response evaluation may be replaced for the purposes of the statistical rule. All patients considered to have a response (CR or PR) must have imaging studies reviewed centrally at the COG. Centers will be notified by the COG about requests for scans of patients with stable disease. Preliminary assessment of activity using institutionally provided tumor measurements will be entered into CDUS quarterly. The central review by COG will be provided as the final reviewed assessment of response when such becomes available.

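### Does the 20-patient primary cohort need a futility look before all 20 patients are assessed?

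*Combined protocol and SAP*

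**What the plan says.** Section 11.3 names a single-stage A'Hern design for the primary cohort. Section 11.3.1 gives its parameters: "a sample of N=20 will provide 90% power to detect an improvement in response rate from 5"% to 25%, alpha 10%, success at 3 or more responses among 20 evaluable patients of any histology. Section 11.1 requires at least 20 evaluable patients, allows for 15% inevaluable and assumes 2 to 9 enrolments per year, so that "the primary cohort of this subprotocol is expected to be completed within 2.7-12 years".

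Section 11 has no interim response boundary. The data are still seen during the trial. Section 11.5 says "Preliminary assessment of activity using institutionally provided tumor measurements will be entered into CDUS quarterly", and adds that "The central review by COG will be provided as the final reviewed assessment of response when such becomes available". Under Section 14.4.1 the monitoring committee meets at least every six months and may recommend changing the study. Section 14.4.2 adds a weekly review by the MATCH chair, vice chair and statistician. Section 10.1 foresees termination by the sponsor.

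**The concern.** The only efficacy decision falls at patient 20, possibly 12 years after opening, and none of the reviews has a stated response criterion. The background evidence makes inactivity a realistic outcome. Section 2.4.1 reports no objective responses in the earlier pediatric phase 1 trials and suggests that this "may have been, in part, because these trials were conducted without genomic pre-selection of treatment subjects". Selection by HRAS has not worked everywhere either: in the adult HRAS-mutant study, "Cohort 1 (HRAS-mutant thyroid cancer) has been closed to active accrual due to lack of efficacy", and all stage 1 responses in the second cohort were in head and neck squamous cell carcinoma (Section 2.3.1.2).

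If the drug is inactive, up to seven more children might be enrolled after 13 consecutive failures. The exact power slightly exceeds 90%, so an early look appears to cost nothing in sample size or stated error rates.

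**Working it through.** **Inputs.** From Section 11.3.1: N = 20, success at 3 or more responses, null rate 5%, target rate 25%. From Section 11.1: 2 to 9 patients per year, 15% inevaluable. The 0/13 look is a hypothetical addition and is not in the documents.

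**1. The plan's own figures (exact binomial).**
- Alpha = 1 − [0.95^20 + 20(0.05)(0.95^19) + 190(0.05²)(0.95^18)] = 1 − (0.3585 + 0.3774 + 0.1887) = 0.0755.
- Power = 1 − [0.75^20 + 20(0.25)(0.75^19) + 190(0.25²)(0.75^18)] = 1 − (0.0032 + 0.0211 + 0.0670) = 0.9087.
- A search over smaller N and all cut-offs finds none with exact alpha at most 10% and power at least 90%, so N = 20 with a cut-off of 3 is the smallest such design.
- Duration: 20/0.85 rounds up to 24; 24/9 = 2.7 years and 24/2 = 12 years, as stated.

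**2. What a stop at 0/13 would do.** Success is lost only if there are no responses in 13 and at least 3 in the last 7.
- Alpha: 0.0755 − 0.95^13 × P(at least 3 of 7 at 5%) = 0.0755 − 0.5133 × 0.0038 = 0.0736.
- Power: 0.9087 − 0.75^13 × P(at least 3 of 7 at 25%) = 0.9087 − 0.0238 × 0.2436 = 0.9030.
- Chance of stopping: 51.3% at a 5% rate, 2.4% at 25%.
- Mean saving at a 5% rate, before overrun: 0.5133 × 7 = 3.6 patients.
- A look at 0/12 gives power 89.86%, so 13 is the earliest zero-response look that keeps 90%.

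**3. The saving after overrun.** Section 8.1 schedules scans as "Every other cycle x 3 then q 3 cycles", and "Tumor Disease Evaluation should be obtained on the next consecutive cycle after initial documentation of either a PR or CR". Two scheduled scans take 16 weeks; three scans plus a confirmatory one take 24 + 4 = 28 weeks. Both are assumed readout times, as is a 26-week wait for a committee meeting on top of 16 weeks (42 in all). Overrun m = rate × weeks/52, rounded to whole patients. If a response among the overrun patients reopens accrual, closure stands with probability 0.95^(13+m), and the mean saving is 0.95^(13+m) × (7 − m).

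| Accrual | Readout | Overrun | Closure stands at 5% | Mean saving at 5% |
|---|---|---|---|---|
| 2/year | 16 weeks | 0.62, taken as 1 | 48.8% | 2.9 |
| 9/year | 16 weeks | 2.77, taken as 3 | 44.0% | 1.8 |
| 2/year | 28 weeks | 1.08, taken as 1 | 48.8% | 2.9 |
| 9/year | 28 weeks | 4.85, taken as 5 | 39.7% | 0.8 |
| 2/year | 42 weeks | 1.62, taken as 2 | 46.3% | 2.3 |
| 9/year | 42 weeks | 7.27, at least 7 | no effect | 0 |

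In calendar time, with a 16-week readout, that is 2.9/2 = 1.5 years or 1.8/9 = 0.2 years. At the slow rate the look is not early: 13/0.85 = 15.3 enrolments take 15.3/2 = 7.6 years.

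**4. What the look would cost.**
- *Late responses.* If closure is irrevocable and only 90% of eventual responses are visible at the look, power is 89.5%; with 80% visible it is 88.2%. A reversal rule restores power (90.6% with one overrun patient, 90.8% with three). Closure then stands less often and stays provisional, while treatment may run for 26 cycles (Section 5.1).
- *Mixed histologies.* Assume response rates of 45% in responsive histologies and 5% in the rest. With 6 responsive-histology patients among the first 13, P(0/13) = 0.55^6 × 0.95^7 = 1.9%. With 3, it is 0.55^3 × 0.95^10 = 10.0%.
- *Precision.* The upper 90% Wilson limit with no responses is z²/(n + z²), with z² = 2.706: 17% at 0/13 against 12% at 0/20.

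**The case for a change.** The strongest case for a look is that it fits within the sponsor's own design. It cannot raise the type I error, it keeps N and the cut-off, and it uses only about 0.6 points of power. After 0/13 the trial is almost lost if the drug is inactive: the chance of 3 or more responses in the last 7 is 0.4% at a 5% rate. These are children with relapsed or refractory disease who may not receive other anticancer therapy on protocol (Section 7.1). Response data already go to CDUS each quarter, so the extra reporting would be small.

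Much of this stands. Section 11 has no numeric futility criterion, and at 2 patients per year the mean saving is worth about a year and a half. A sponsor could adopt such a rule without embarrassment.

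It does not show that the plan is deficient. At a 25% rate, 24.4% of trials at 0/13 would still reach 3 responses. The primary aim in Section 1.1 is to determine the response rate, with progression-free survival and tolerability as secondary aims, and all three are better served by 20 patients. Section 11.3.2 makes the histology expansion cohorts depend on responses in the primary cohort, so closing it removes that route. Nor is the trial unable to react: the monitoring committee, the weekly leadership review and sponsor termination are all provided for. What is missing is a number, not a mechanism.

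**Conclusion.** The concern does not hold. The stated 10% and 90% are met exactly (7.55% and 90.87%), the duration range reproduces, and the single-stage design is stated openly. No number or rule in Section 11 is wrong.

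A futility look is a trade-off on which competent statisticians would differ. Its benefit arises only if the drug is inactive, and averages from none to about 3 patients depending on accrual and readout. Its costs are a less precise response rate, less secondary information, loss of the expansion route and a risk of premature closure that depends on the order in which histologies enrol.

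The savings rest on a uniform 5% null rate, accrual continuing during the look, and the assumed waits of 16, 28 and 42 weeks. The 10.0% risk of a misleading 0/13 rests on the assumed 45% and 5% response rates. The master screening protocol, APEC1621SC, is not among the documents, so a futility provision there cannot be ruled out; the conclusion does not depend on one.
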